Aim 2: Compare the cost-effectiveness of four conditions to promote CRC and BC screening among women ages 50 to 75: 1) usual care; 2) a TIWeb; 3) a CSC, and 4) a TIWeb + a CSC. Two groups of women will be included. **Group A** includes women who are nonadherent to CRC screening but adherent to BC screening and **Group B** includes women nonadherent to both CRC and BC screening.

Aim 3: Examine differences in intervention effects by knowledge, cancer screening beliefs, health status, demographic variables (age, race, education, and marital status), screening history, out-of-pocket costs for screening, baseline stage of adoption, health care site, and participant involvement in the intervention.

Hypothesis 1: *Interactions will be observed when intervention effects are examined by knowledge, cancer screening beliefs, health status, demographic variables (age, race, education, and marital status,), provider recommendation, screening history, out-of-pocket costs for screening, baseline stage of adoption, provider recommendation, and participant involvement in the intervention.*

Hypothesis 2: *Women receiving care at primary care practices that have on-site colonoscopy available will have greater CRC adherence than women receiving care at sites where on-site colonoscopy is not available.*

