We will use a total of eight practice sites of which four have colonoscopy available on site and four that must schedule colonoscopy at other locations. The first four sites with colonoscopy facilities have approximately **8,500** women patients who are between the ages of 50 and 75. The second four sites without colonoscopy have **8,700** potentially eligible women patients for a total of **17,200** women. According to our prior data approximately 26% are nonadherent to CRC but adherent to BC (**n=4472**) and 44% are nonadherent to both (**n=7568**). Our study requires **1588** women for **Group A** (nonadherent to CRC) and **Group B** (nonadherent to both CRC and BC screening) total (**see Section D.1.2**). Assuming a 50% acceptance rate, we will contact **3176** total for both groups. Although there will be some participants who cannot be contacted because of recent moves or change in telephone numbers, our past work (**Preliminary Studies**) has shown that fewer than 13% would be lost to follow-up or because of change in insurance. In a current ongoing study, we have found that up to 30% of phone numbers are incorrect, reflecting increased use of cell phones. Assuming the worst case scenario of 30% incorrect numbers, we will have more than adequate numbers to enroll the total of **1588** women.

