Group A (nonadherent to CRC but adherent to BC screening guidelines)

Hypothesis 1- Efficacy Analysis: The differences in binary adherence across the four randomized arms will be tested initially with the chi-square test for a 2x4 cross-classification table (adherence by randomized intervention groups). Binary logistic regression analysis, with three dummy variables using usual care as the reference category, will be computed to study the effects of each intervention (TIWeb, CSC, TIWeb +CSC) versus usual care on adherence, while adjusting for any potentially confounding covariates. In addition, model contrasts will be specified to statistically compare each of the three intervention arms to the others. Since the intervention is delivered to the patient and not the provider, analysis of variation in CRC screening by practitioners will be limited. Outcomes of patients who share the same providers may be slightly more correlated than outcomes of patients from different providers. Thus, the within-provider correlation among patients will be assessed with variance components, and if necessary generalized estimating equations (GEE) will be used with logistic regression to account for the within-provider correlation. We will enter as independent variables into logistic models the following: randomized group membership and any demographic covariate (age, race, education, marital status, screening history, baseline stage of adoption, SF12 mental health component, SF12 physical health component) for which the randomized groups differ significantly at baseline using a liberal significance level of 0.20. We will also measure whether subjects report that their physicians have recommended the screening test in the past and the amount of out-of-pocket expense for screening and enter these as covariates. In addition to demographic variables, other potential covariates will be location of TIWeb intervention (use of a computer at home or elsewhere), and whether women in the TIWeb group needed technical help from the research assistant to use the TIWeb program. We plan to include screening history as a covariate in our analysis by using the total number of past screenings for each test since the participant turned 50. For analysis with mammography screening, one covariate will be included (total number of mammograms since age 50). For the analysis of CRC screening, two covariates will be included simultaneously in the models (total number of FOBTs since age 50, and "any previous endoscopic test" [yes/no]). The CRC screening analysis requires two covariates because a history of five FOBTs, for example, is not equivalent to one previous FOBT and one previous colonoscopy or sigmoidoscopy. All variables in the

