The effects on the ICERs of methods and parameter uncertainty will be assessed by one-way and/or multi-way sensitivity analysis. For example, ICERs may be sensitive to wage rates of key personnel and the overhead rates. Statistical uncertainty in the cost-effectiveness ratios will be assessed with 1,000 bootstrap samples. The outcome of each bootstrap sample will be expressed as a point on a scatter plot of incremental costs and percent screened and reflects the uncertainty arising from the model parameters. Scatter plots of the incremental costs and effects will be used to define the 95% confidence limits around the cost-effectiveness ratios.⁽¹⁴⁶⁾

Aim 3: Interaction analysis.

Hypothesis 1 Interactions: We will use interaction terms in the logistic regression models, developed above for analyses of Aim 1, to test whether intervention effects depend on knowledge, cancer screening beliefs, health status, demographic variables (age, race, education, and marital status), screening history, out-of-pocket costs for screening, baseline stage of adoption, provider recommendation, and participant involvement in the intervention. We will also test the interaction between each intervention and whether participants sought help through additional contact(s) with the research assistants. If an interaction is significant, we will use parameter estimates from the logistic regression model to estimate odds ratios for intervention effects at various levels or scores of the interacting covariates (e.g., within each race or site, or at various values, for example quartiles, of perceived barriers). Because many interactions will be tested, we will adjust for multiple comparisons (see below).

Hypothesis 2 Site Differences: We will compare screening adherence between the group of women who receive care in sites that have colonoscopy available with those who are not in such sites using logistic regression after adjusting for randomized group (usual care, TIWeb, CSC, and TIWeb + CSC).

Adjustment for multiple comparisons: Because many tests will be performed in Exploratory Aim 3, we will report p-values adjusted for multiple comparisons in the analyses, using the resampling step-down adjustment method of Westfall and Young,⁽¹⁴⁷⁾ which accounts for the dependence structure between related tests.

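### The on-site colonoscopy hypothesis compares four practices with four, but the planned test treats about 1,430 women as independent

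*Combined protocol and SAP*

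**What the plan says.** Section A, Aim 3, Hypothesis 2 is directional: "Women receiving care at primary care practices that have on-site colonoscopy available will have greater CRC adherence" than women at the other sites. Section D.3 fixes the units: "eight practice sites of which four have colonoscopy available on site and four that must schedule colonoscopy at other locations". Section D.13, under Hypothesis 2 Site Differences, compares the two groups of women "using logistic regression after adjusting for randomized group (usual care, TIWeb, CSC, and TIWeb + CSC"). Randomized arm is the only adjustment named, and there is no site term, cluster-robust variance or site-level analysis.

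Clustering appears in one other place, the Aim 1 efficacy analysis in D.13: "the within-provider correlation among patients will be assessed with variance components, and if necessary generalized estimating equations (GEE) will be used with logistic regression". That step concerns providers and is conditional. The paragraph explains its limited treatment of practitioners this way: "Since the intervention is delivered to the patient and not the provider, analysis of variation in CRC screening by practitioners will be limited". The Aim 1 models are carried forward for Aim 3, Hypothesis 1 ("We will use interaction terms in the logistic regression models, developed above for analyses of Aim 1"), but this is not said for Hypothesis 2. Aim 3 p-values are then to be adjusted by the Westfall and Young step-down method, and that paragraph calls the aim exploratory.

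**The concern.** On-site colonoscopy belongs to the practice, not to the woman. Every woman at a site has the same exposure, so there are eight independent observations of it, however many women enroll. Patient-level logistic regression computes its standard error as if each woman supplied separate information. Chance differences between practices in case mix, insurers or physician habits then pass for evidence about colonoscopy access.

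The documents give reason to expect such differences. D.1 says usual care depends on the practice setting, and D.11 says scheduling depends on the physician's location. Adjusting for arm removes none of this, because arms are randomized within the trial and not aligned with sites.

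Nothing else in the plan repairs the test. The argument that the intervention is delivered to the patient protects the arm comparison but does not apply to a site-level exposure. Provider clusters, if carried over, would leave correlation between providers at the same site unmodelled. The step-down adjustment handles dependence between tests, not between women, and it takes the p-value as given. The trial could therefore report a benefit of on-site colonoscopy that reflects nothing but ordinary variation between practices.

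**Working it through.** **Inputs.** From D.3: 8 sites, 4 versus 4. The two sets have similar pools (8,500 and 8,700 women), so I take equal site sizes. From D.12: 357 women per arm at 6 months and adherence of 20%, 30%, 40% and 55%. Assumed: two-sided alpha 0.05 (not stated), and a site ICC from 0.001 to 0.05 (not given).

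**The plan's own figures.** With 357 per arm, a two-sided 5% test of two proportions gives power 0.871 (arms 1 v 2), 0.801 (2 v 3) and 0.981 (3 v 4), and above 0.999 for the other pairs. This reproduces the D.12 table (.87, .80, .98, .99). Also 357/0.90 = 397. D.12 gives no power for Hypothesis 2.

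**What the planned test assumes.** N = 4 x 357 = 1,428, or 714 per site type. Mean adherence is (20 + 30 + 40 + 55)/4 = 36.25%. The unclustered standard error of the difference is sqrt(2 x 0.3625 x 0.6375/714) = 0.0254, which implies a detectable difference of about 7.1 points at 80% power.

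**Effect of site clustering.** Women per site: m = 1,428/8 = 178.5. Then:
- SD of true site adherence = sqrt(ICC x 0.3625 x 0.6375)
- Design effect = 1 + 177.5 x ICC
- Effective N = 1,428 / design effect
- Type I error of the planned test = 2 x [1 - Phi(1.96 / sqrt(design effect))]
- Detectable difference from a valid test: noncentral t, 6 df, with standard error 0.0254 x sqrt(design effect)

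| ICC | Site SD (points) | Design effect | Effective N | Type I error | Detectable difference (points) |
|---|---|---|---|---|---|
| 0.001 | 1.5 | 1.18 | 1,213 | 7% | 9.3 |
| 0.005 | 3.4 | 1.89 | 757 | 15% | 11.8 |
| 0.01 | 4.8 | 2.78 | 515 | 24% | 14.3 |
| 0.02 | 6.8 | 4.55 | 314 | 36% | 18.3 |
| 0.05 | 10.7 | 9.88 | 145 | 53% | 26.9 |

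**Check by simulation.** Eight sites, normal site effects on the logit scale, no true effect of colonoscopy access, 2,000 runs per ICC, fitting the planned model. Here the ICC is on the latent (logit) scale, so these rows must not be read against the table above at the same ICC. To convert: site variance = ICC/(1 - ICC) x pi^2/3, and observed-scale ICC is roughly that variance times the mean of p(1 - p) over the four arms, 0.2144. At latent ICC 0.01, the variance is 0.0332, the observed ICC is 0.0332 x 0.2144 = 0.0071, the design effect is 1 + 177.5 x 0.0071 = 2.26, and the predicted error is 19%.

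| Latent ICC | Observed ICC | Predicted error | Simulated error, planned model |
|---|---|---|---|
| 0 | 0 | 5% | 4.7% |
| 0.005 | 0.0035 | 12.5% | 13% |
| 0.01 | 0.0071 | 19% | 19% |
| 0.02 | 0.0144 | 30% | 30% |
| 0.05 | 0.0371 | 48% | 46% |

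Formula and simulation agree once the scales are matched. In the same runs a t-test on the eight arm-adjusted site means rejected 4.5% to 5.5% of the time. Generalized estimating equations (GEE) clustered by site, with an uncorrected sandwich variance, rejected 13% to 15% of the time, even at ICC 0. Naming GEE is therefore not enough with eight clusters.

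**The case against.** The strongest reply is that the inflation depends on a quantity the documents do not give. If practices did not differ at all, the planned test would be valid, and at ICC 0.001 the error is only about 7%. The one remark on clustering in D.13 says that patients of the same provider may be slightly more correlated. This stands as a limit on the size of the problem, not on its direction. With 178 women per site even a slight correlation matters, and D.1 itself says usual care differs by practice setting.

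Second, the aim is labelled exploratory, Hypothesis 2 did not drive the sample size, and the randomized comparison is untouched because arms vary within sites. That is right, and it lowers the priority. It does not make the p-value valid, and Hypothesis 2 is a stated directional hypothesis whose p-value the plan intends to report.

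Third, a site-level analysis corrects the variance, not the confounding: practices with on-site colonoscopy may differ systematically from those without. This also stands, and is why the result should be reported as non-randomized.

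Fourth, the valid test is weak. At a true difference of 7.1 points it has about 40% power at ICC 0.005, 29% at 0.01 and 20% at 0.02. An exact permutation test has a smallest two-sided p of 2/70 = 0.029 before any multiplicity adjustment, so even complete separation of the two sets of sites is unlikely to survive the step-down procedure. That reflects the design. Eight sites cannot support a confirmatory test of this hypothesis.

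**Conclusion.** The concern holds. As written, the Hypothesis 2 analysis gives a standard error and p-value that are too small whenever practices differ, and no other part of the plan corrects this. On the observed scale the type I error of the nominal 5% test runs from about 7% at ICC 0.001 to 53% at ICC 0.05, with 15% to 36% between 0.005 and 0.02. These figures assume equal site sizes, 1,428 women and two-sided testing. Unequal sites would raise the design effect, as would a records-based analysis of up to all 1,588 women. The flaw is confined to one exploratory, non-randomized hypothesis. It should be corrected, but it does not threaten the trial's primary result.

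**What to change.** Rewrite the Hypothesis 2 paragraph in D.13 so that the practice is the unit of analysis. Compute arm-adjusted colorectal screening adherence at 6 months for each of the eight sites, compare 4 with 4 by a t-test on 6 degrees of freedom, and give the difference with its 95% interval. An exact permutation test over the 70 possible allocations can accompany it. A logistic mixed model with a random site intercept and small-sample degrees of freedom has the same aim. If GEE is preferred, it must cluster on site and use a small-sample correction. Report the observed site ICC, and state that this is a non-randomized comparison of eight practices, to be read as descriptive.

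This changes only analysis-plan wording and needs no new data, sites or participants. The price is precision: even at ICC 0, moving to 6 df raises the detectable difference from 7.1 to 8.6 points, and at ICC 0.01 it becomes 14.3 points.

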For women who are nonadherent to CRC screening guidelines but adherent to BC screening (Group A), the TIWeb and the CSC will encourage CRC screening by building on the women's success with regular BC screening. For women who are nonadherent to both CRC and BC screening (**Group B**), the TIWeb and the CSC interventions will promote both CRC and BC screening simultaneously. Research indicates that individuals who undergo one type of cancer screening are more likely to pursue other forms of screening,⁽¹³⁾ making a holistic approach to cancer screening efficient and consistent with what would happen in a routine preventive care visit. In the proposed study, we also will test the cost-effectiveness of each intervention arm and the intervention interactions with demographic and practice variables. Past research^(14, 15) has shown that interventions vary in both cost and efficacy, making the addition of cost-effectiveness analysis important for future translation to practice. We will use a 2X2 factorial design with women randomly assigned to receive one of the following: 1) usual care, 2) a TIWeb, 3) a Cancer Screening Call (CSC), or 4) a TIWeb plus a CSC.

Aim 1: Compare the efficacy (adherence and stage) of four conditions to promote CRC and BC screening among women ages 50 to 75: 1) usual care; 2) a mailed TIDVD; 3) a CSC, and 4) a mailed TIDVD + a CSC. All women will be non adherent to CRC screening and may or may not be adherent to BC screening. 50 **Group A (nonadherent to CRC screening guidelines but adherent to BC screening guidelines)**

Hypothesis 1 (Primary outcome): There will be differences in CRC screening adherence and stage of adoption, when controlling for adherence to BC screening at baseline, among women who are randomized to 1) usual care; 2) a TIWeb; 3) a CSC, and 4) a TIWeb plus a CSC.

Group B (nonadherent to both CRC and BC screening guidelines)

Hypothesis 2 (Secondary outcome): In the group that is nonadherent to both CRC and BC screening at baseline, there will be differences in adherence to both CRC and BC screening and stage of adoption, among women who are randomized to 1) usual care; 2) a TIWeb; 3) a CSC, and 4) a TIWeb plus a CSC.

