The common variables that will be used to deliver simultaneous messages originate in the Health Belief Model (HBM) and the Transtheoretical Model of Behavior Change (TTM)-both of which have demonstrated efficacy with single behaviors. The multiple behavior theoretical approach will build on this previous work by identifying the common variables that have predicted behavior change and applying these tailoring of these variables simultaneously to CRC and BC screening. The variables have been integrated into a conceptual framework that will guide the proposed study (see **Figure 1**) and include: perceived risk, perceived benefits and barriers to a health behavior and self-efficacy to accomplish the behavior.^{(108, 109), (110)} The belief variables of perceived risk, perceived benefits and barriers, and perceived self-efficacy have been used in previous interventions and found

to predict both CRC and BC screening behavior.^(14, 38, 40, 43, 50, 111) Antecedent variables are identified in the HBM and include knowledge, age, education, and marital status, all of which have been related to both CRC and BC screening.^(1, 53, 112-114) Race has been included as a demographic variable given the relatively greater mortality from both cancers in African American women. Although research has focused only on the most recent history of a behavior, we will also incorporate the lifetime screening behavior for CRC and BC. Changing or initiating a health action involves a gradual change in decisional balance between the pros (benefits) and cons (barriers). In our proposed interventions, decisional balance will be addressed through communication directed toward the perceived benefits and barriers for the specific screening tests needed by each individual recipient. (See **Appendix A**)

Figure 1. Theoretical Framework

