D.1. Research Design. We propose a prospective randomized 2X2 factorial design: 1) usual care; 2) aTIWeb; 3) a Cancer Screening Call (CSC), and 4) a TIWeb + a Cancer Screening Call (CSC). The intervention will be tested in two groups of women. **Group A** will include women who are nonadherent to CRC but adherent to BC screening guidelines. **Group B** will include women who are nonadherent to both CRC and BC screening guidelines. Random assignment to intervention

arms will be performed within both **Group A and Group B**. A periodic list of eligible women will be pulled from databases and sent to the research study office at IUSON. The list will then be forwarded to the co-investigator in charge of recruitment ([name], Executive Director for the Indiana Family Practice Research Network) and the physicians for the opportunity to review their own patient list. This information will consist of name, DOB/age, address, and phone number. An additional field will include mammogram status, indicating whether the individual has a documented mammogram in the past 15 months. Then a letter, brochure, and refusal postcard will be sent to potentially eligible women. A parsed list of women who don't opt out by returning the refusal post card, calling a toll free number, or emailing the project manager (number and email provided on brochure) will be scheduled for a recruitment phone call. Participants in the TIWeb Intervention Arm will be given access to a TIWeb that is programmed to provide an intervention that is interactive and tailored to the participant's individual beliefs and demographics. Individuals receiving the TIWeb will be given information that allows them to call and receive an FOBT kit in the mail or schedule an appropriate CRC test and/or mammogram. The physicians at the recruitment sites will have reviewed the list of potential participants before recruitment to ensure they are candidates for screening tests.

Figure 2. Study Schema

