In Table 8 of the original application (see appendix), we proposed enrolling 327 for each of 8 combinations of 4 arms and 2 groups (A and B) for a study total of 2616. However, using this alternative approach will require only 1308 (327 in each of the 4 arms) women to test the primary outcome of CRC adherence. However, new studies, including our own, indicate 15-20% adherence to CRC screening in control conditions. Our initial proposal anticipated on 10% adherence in the control arm. Thus, although the new design decreases the sample size by combining the groups, a more realistic estimate of the adherence in the control group will actually increase the sample size compared to our estimate in Group A for the initial proposal. Specifically, we propose to increase our estimate of CRC adherence in all four arms, to accommodate a change in the proposed adherence in the control group from 10% to 20%. This will require 397 instead of 327 per arm (see Table 1). Thus, a sample of 397 per group at baseline (357 per group at 6 months after 10% estimated attrition) will provide 80% power to detect differences between any pair of the four randomized arms for Aim 1 (Table 1).

Revised Sample size and Power analysis for primary efficacy hypothesis of estimated CRC screening adherence rates in the combined groups of those adherent (Group A) and non-adherent (Group B) at baseline to breast cancer screening (Aim 1, primary outcome of CRC adherence)

GROUPS A and B combined

Time	Usual Care (1)	TIDVD (2)	CSC (3)	TIDVD+CSC (4)	Power
Baseline adherence	0%	0%	0%	0%	NA
Total sample size (N):	(n = 397)	(n = 397)	(n = 397)	(n = 397)	
N by baseline strata, Adherent to BC (A) Non-adherent to BC (B)	(n = 119) (n = 278)				
6 months adherence	20%	30%	40%	55%	Power for 357/arm (Groups A and B combined)
Total sample size (N):	(n = 357)	(n = 357)	(n = 357)	(n = 357)	1v2 .87 1v3 .99 1v4 .99 2v3 .80 2v4 .99 3v4 .98
N by baseline strata, Adherent to BC (A) Non-adherent to BC (B)	(n = 107) (n = 250)				

Enrollment will be stratified by women adherent to breast but not CRC screening and those adherent to neither in a 30%/70% ratio so that we will have an adequate sample to detect an 80% power for Aim 2. Aim 2 will use only the subgroup of women who are not adherent to either breast or CRC screening. This will provide at least 80% power for Group B for comparing each pair of randomized arms, when testing the secondary outcome (adherence to both CRC and BC screening) (Table 2).

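### The exploratory comparison of practices with and without on-site colonoscopy adjusts only for randomized arm, so any case-mix difference between the two sets of practices would bias the site estimate

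*Combined protocol and SAP*

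**What the plan says.** Section A (Aim 3, Hypothesis 2) predicts that women at "practices that have on-site colonoscopy available will have greater CRC adherence than women receiving care at sites" without it. D.3 describes "a total of eight practice sites of which four have colonoscopy available on site and four that must schedule colonoscopy at other locations". D.13 (Aim 3, Hypothesis 2 Site Differences) gives the whole model: adherence is compared between the two kinds of site "using logistic regression after adjusting for randomized group (usual care, TIWeb, CSC, and TIWeb + CSC"). The next paragraph of D.13 calls Aim 3 exploratory and promises Westfall-Young adjusted p-values.

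Four other places bear on this.

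- **Randomization.** D.1 has individual women randomized to arm within Group A and within Group B. It states no stratification by practice.
- **Group mix.** D.12 says "Enrollment will be stratified by women adherent to breast but not CRC screening and those adherent to neither in a 30%/70% ratio". That ratio is for the trial; none is given by practice or site type.
- **Prognostic variables.** Section A says "individuals who undergo one type of cancer screening are more likely to pursue other forms of screening", which is the distinction between Groups A and B. The theoretical framework in Section B lists "knowledge, age, education, and marital status, all of which have been related to both CRC and BC screening". Group status is fixed at recruitment (D.4), and Table 7 has demographics and knowledge collected at baseline.
- **Covariate rules.** D.12 enters Group A/B in the Aim 1 model for CRC adherence. D.13 admits demographics, screening history, baseline stage and SF-12 scores when the randomized groups differ at the 0.20 level.

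**The concern.** Site type is an observational exposure. To confound the comparison a variable must differ between the two sets of practices and predict CRC adherence. Randomized arm meets the second condition but, in expectation, not the first. The variables that could meet both are left out.

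Nothing elsewhere in the plan puts them back. Hypothesis 1 of Aim 3 is built on the Aim 1 models; Hypothesis 2 has its own model and is not tied to them. A large imbalance between site types with well-balanced arms would bring no covariate in. The multiplicity adjustment deals with the number of tests, not with bias. The limitations listed at the end of Section D do not mention differences between practices.

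At stake is a directional hypothesis, reported with a p-value, whose result could reflect who attends the practices rather than what they offer. Bias in the other direction could hide a real difference.

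**Working it through.** **The plan's own figures.** D.12 gives no power or effect size for the site comparison. Its design inputs do reproduce. With 357 per arm and two-sided 0.05 (assumed, as D.12 states no level), power for 30% v 40% is Φ[(0.10 − 1.96 × √(2 × 0.35 × 0.65/357)) / √((0.30 × 0.70 + 0.40 × 0.60)/357)] = Φ[(0.1000 − 0.0700)/0.0355] = 0.80, as stated. Also 357/0.90 = 397 per arm and 4 × 397 = 1588. This confirms the inputs and does not itself bear on the point.

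**Inputs for the illustration.**
- From D.12: 4 × 357 = 1428 women at 6 months; adherence of 20%, 30%, 40% and 55%, mean 145/4 = 36.25%; Group A share 30%.
- Assumed: an even split, 714 per site type (D.3 gives 8,500 and 8,700 women at the two sets of practices); independent women; no true site effect.
- Not in the documents, so ranged: the A v B odds ratio for CRC adherence (1.5 to 2.0) and the difference in Group A share between site types (10 to 30 points).

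**Step 1.** Solve 0.30 × pA + 0.70 × pB = 0.3625 with the odds ratio fixed. Odds ratio 1.5 gives pA = 42.9% and pB = 33.4%, a gap of 9.5 points. Odds ratio 2.0 gives 47.7% and 31.3%, a gap of 16.4 points.

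**Step 2.** Spurious site difference δ = (pA − pB) × difference in Group A share.

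**Step 3.** SE = √(2 × 0.3625 × 0.6375/714) = 0.0254. Rejection probability = Φ(δ/SE − z) + Φ(−δ/SE − z), with z = 1.96 at 0.05.

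**Step 4.** For a rough view of multiplicity, D.13 lists 12 interaction variables, plus contact with research assistants, plus the site test: 14 tests if each counts once. Bonferroni, a conservative stand-in for Westfall-Young, gives 0.05/14 = 0.0036.

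| A v B odds ratio | Gap in Group A share | Spurious difference | Rejection at 0.05 | Rejection at 0.0036 |
|---|---|---|---|---|
| 1.5 | 10 points | 1.0 point | 7% | 0.6% |
| 1.5 | 20 points | 1.9 points | 12% | 1.5% |
| 2.0 | 20 points | 3.3 points | 25% | 5% |
| 2.0 | 30 points | 4.9 points | 49% | 16% |

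**Check by simulation.** Logistic models were fitted in 1,500 simulated trials with the four arm rates, Group A shares of 40% v 20%, odds ratio 2.0 and no site effect. The site odds ratio was 1.13 with no adjustment and 1.14 adjusted for arm (23% rejection). Adding Group A/B gave 1.00 (5.4% rejection). So arm adjustment removed none of the bias and the omitted factor removed it. With equal shares (30% v 30%) the arm-only odds ratio was 1.00 and rejection 4%.

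**The case against.** The strongest objection is that a long covariate list could do harm. Women are eligible because they are already patients of these practices (D.2), so exposure to on-site colonoscopy precedes baseline. Screening history, which in D.13 includes any previous endoscopic test, and baseline stage, which in Table 6 depends on intention to be tested, may be consequences of that access. Forcing them into the main model could adjust away part of the difference being studied. This stands. It is why the main model should be limited to Group A/B and demographics, with the doubtful variables kept for sensitivity analysis.

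Second, the aim is exploratory and its p-values are adjusted. This also stands: the unadjusted rejection rates are not those of the reported test. The bias in the estimate and its interval is untouched.

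Third, the illustration rests on assumed gaps. Nothing in the documents suggests a 20 or 30 point difference in Group A share, and the direction is unknown. A reader might infer that the site result will be biased, or biased in favour of the hypothesis. The documents support neither.

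Fourth, a reader might infer that the plan claims a causal effect of on-site colonoscopy. It does not: the hypothesis is worded as a difference between groups of women and the analysis is headed as site differences. A reader might also infer that adjusting for arm is an error. It is not, since the planned rates run from 20% to 55% across arms and chance imbalance across practices remains possible. It is insufficient rather than wrong.

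Finally, with four practices per side, differences at practice level stay confounded with site type whatever individual covariates are added. This limits the gain from the fix but does not argue against removing the measured part.

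**Conclusion.** The point holds as a conditional one. The planned model takes no account of measured case-mix between site types, and no other rule in the plan supplies the adjustment. If Group A share or demographics differ between the two sets of practices and predict CRC adherence, the site estimate is biased; if they do not differ, it is not. Within the assumed ranges the spurious difference is 1.0 to 4.9 percentage points, from Group A/B alone and before any clustering by practice. The 7% to 49% rejection range applies to an unadjusted 0.05 and falls to about 0.6% to 16% under the 14-test stand-in. These figures illustrate what the model would let through; they do not estimate this trial's error rate. The exploratory label lowers the weight of the point, but the correction is cheap and worth making before the data are seen.

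**What to change.** In D.13, Aim 3 Hypothesis 2:

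- Model CRC adherence on site type, randomized arm, Group A/B, age, race, education and marital status, all entered regardless of p-value. Report the arm-only estimate beside it.
- Tabulate baseline characteristics by site type.
- Add screening history, baseline stage, knowledge and SF-12 scores in a further sensitivity model only, with the reason stated: history and stage in particular may reflect earlier on-site access.
- Leave out provider recommendation and out-of-pocket cost, which may lie on the pathway from on-site availability to screening.
- Describe the result as an association.

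The cost is a few lines in the plan, one extra table and a slightly longer model. All the variables are already collected. Unmeasured differences between practices remain, and the report should say so.
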